12.1.3. Secondary Endpoints

- Reduction in the progression to acute respiratory failure [Time Frame: 15 days]
- Patients with a baseline PaO₂/FiO₂ ≥ 200: progression of respiratory failure is defined by:
 - a. severe gas transfer deficit (PaO₂/FiO₂ < 200);
 - b. persistent respiratory distress while receiving oxygen (persistent marked dyspnea, use of accessory respiratory muscles, paradoxical respiratory movements);The rate will be calculated as the proportion of patients who experienced at least one of the events above by day+15 from treatment start.
- Overall survival and all-cause mortality (day 15, day 28).
- Time to improvement in oxygenation for at least 48 hours. Improvement in oxygenation is defined as an increase in PaO₂/FiO₂ of 50 (or greater) compared to the nadir of PaO₂/FiO₂.
- Number of patients requiring mechanical ventilation, if not on mechanical ventilation at study entry.
- Reduction in progression to acute respiratory failure [Time Frame: 28 days]
- Change in the WHO COVID-19, “8-point ordinal scale” from study entry to day 28 (Table 1). To be assessed on day 3, day 8, day 15, day 28.
- Duration of hospitalization and duration of ICU care.
- Toxicity assessment (including incidence of grade 3-5 hemorrhagic events).
- Change in D-dimer [Time Frame: baseline, study day 3, day 8, day 15, and day 28]. Changes in plasma D-dimer level compared with baseline at enrollment.
- Decrease or Change in IL-6:IL-10 ratios.
- Free-Days- at day 28
 - Oxygen
 - Ventilator
 - Vasopressor
 - ICU
 - Hospitalization

Table 1: WHO Ordinal scale Ordinal Score:

Patient State	Descriptor	Score
Ambulatory	No limitation of activities	1
	Limitations of activities	2
Hospitalized (mild disease)	No oxygen therapy	3
	Oxygen by mask or nasal prongs	4
Hospitalized (severe disease)	Non-invasive ventilation or high-flow oxygen	5
	Intubation and mechanical ventilation	6
	Mechanical ventilation + additional organ support – pressors, RRT, ECMO	7
Dead	Death	8

Exploratory Endpoints

- Soluble E-selectin and P-selectin levels compared with baseline at enrollment.
- Thrombosis free days (clinically defined) at day 28.
- Change in other cytokine levels, endothelial or leukocyte activation (day 1, 15, 28) in IL-6, IL-10, TNF-alpha and Angiopoietin-2.

12.2 Sample Size and Accrual

This is a pilot proof of concept feasibility study. 15 patients who consent to drug administration will be enrolled in the treatment arm.

The sample size determination was not based on statistical power analysis but is large enough to provide adequate information regarding safety, and to contribute to the design of subsequent studies, and is the number of patients that we can expect to accrue in the current setting of the SARS-CoV2 pandemic.

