12 STATISTICAL CONSIDERATIONS

12.1 Study Design/Study Endpoints

This is a prospective, interventional, single-arm, open label trial, with 1:1 matched de-identified retrospective control cohort. Study subjects will receive uproleselan IV BID x 7 days. 15 patients who consent to drug administration will be enrolled in the treatment arm.

Primary Endpoints: Safety

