12.3 Data Analyses Plans

Descriptive statistics will be calculated for quantitative safety data, as well as change from baseline. Frequency counts will be compiled for classification of qualitative safety data.

Secondary endpoints include reduction in the progression to acute respiratory failure. For patients with a baseline PaO₂/FiO₂ \geq 200: progression of respiratory failure is defined by:

- severe gas transfer deficit (PaO₂/FiO₂ < 200);
- persistent respiratory distress while receiving oxygen (persistent marked dyspnea, use of accessory respiratory muscles, paradoxical respiratory movements);

The rate will be calculated as the proportion of patients who experienced at least one of the events above by day+15 from treatment start.

There are many other secondary endpoints, but two of the most important are: (i) Day 28 overall survival and (ii) Day 28 ventilator free survival, both of which are binary endpoints. Day 28 overall survival will be summarized by the proportion of the twelve patients who are alive at Day 28 after starting treatment, and Day 28 ventilator-free survival will be summarized by the proportion of the twelve patients who are both alive and not using a ventilator at Day 28 after starting treatment. Both proportions will be

accompanied by an exact 95% confidence interval. All other secondary endpoints will be collected and assessed.

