13 STUDY STOPPING RULES

Additional Interim Safety Assessment (Study Sample Size: 15 patients)

An interim assessment for toxicity and early mortality will be performed after the first 5 patients have enrolled, and again after the first 10 patients are enrolled. Accrual may proceed to a maximum of 15 patients, if the stopping rules are not met within the first 5 patients

The study may be halted for further review if, for any reason involving subject safety, the PIs and Medical Monitors deem continuing the study inappropriate. The following scenarios will also result in temporarily halting the study for further review: 1) major bleeding event in more than 2 of first 10 patients on protocol (as defined as fatal bleeding and/or symptomatic bleeding in a critical area or organ, such as intracranial, intraspinal, intraocular, retroperitoneal, intraarticular or pericardial, or intramuscular with compartment syndrome and/or bleeding causing a fall in hemoglobin level of 2g/dL or more, or leading to transfusion of two or more units of whole blood or red cells). This bleeding definition is congruent with International Society of Thrombosis and Hemostasis (ISTH) definition of major bleeding. An incidence of > 20% hemorrhagic complications would be unacceptable in this setting. Thus, we will continually monitor the observed proportion of patients with major bleeding complications. We start with prior Beta distribution, which has mean 0.2. If ever we have more than 80% posterior probability that the true proportion is greater than 0.20, accrual to the protocol will be suspended to allow the MM and PIs to review the incidence of major bleeding. 2) We will also continually monitor the study for excessive Day 15 mortality. In parallel with our decision rule related to excessive severe hemorrhagic events, we will suspend accrual if we see if we see at least five deaths by Day 15 among the first six patients, or at least seven deaths by Day 14 among the first eleven patients. If the true Day 14 mortality rate is 70% (which is the historical rate for patients with respiratory compromise), the study has a probability of 0.80 of being suspended. Conversely, if the Day 14 mortality rate is 50%, the study has a much lower probability of 0.30 of being suspended.

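### The plan calls 15 patients adequate for safety without a precision figure, and gives event-type primary safety data counts while two secondary endpoints get exact 95% intervals

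*Combined protocol and SAP*

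**What the plan says.** Section 12.1 states "Primary Endpoints: Safety" and attaches no event rate, target or precision to it. On size, section 12.2 says "15 patients who consent to drug administration will be enrolled in the treatment arm" and then, after stating that no power calculation lies behind that number, calls it "large enough to provide adequate information regarding safety". The statistical methodology entry of the synopsis makes the same claim. Neither place gives a number behind it.

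Section 12.3 has two sentences on safety. For measurements: "Descriptive statistics will be calculated for quantitative safety data, as well as change from baseline". For events: "Frequency counts will be compiled for classification of qualitative safety data". No interval is named for any safety proportion. The same section says that two secondary endpoints, survival and ventilator-free survival at Day 28, will be "accompanied by an exact 95% confidence interval", and it computes both over twelve patients rather than 15. The incidence of grade 3-5 bleeding is listed as a secondary endpoint in 12.1.3, but it falls under the closing sentence of 12.3, which names no method for the remaining secondary endpoints.

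Section 13 supplies the one benchmark for bleeding: "An incidence of > 20% hemorrhagic complications would be unacceptable in this setting". It is tied to major bleeding on the ISTH definition. Accrual is suspended for review if more than 2 of the first 10 patients bleed, or if the posterior probability that the rate exceeds 0.20 passes 80%, starting from a Beta prior with mean 0.2 whose parameters are not given.

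**The concern.** Two things do not fit together. The plan says the sample is adequate for its primary purpose but does not say how precisely 15 patients measure any safety rate. And the primary endpoint, where it consists of events, is reported with less information about uncertainty than two secondary endpoints.

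What is at stake is how the result is read. The likely final statement is a small count, such as no major bleeds or one among 15. Without an interval, either looks reassuring, and the reader cannot set it against the 20% that the plan itself calls unacceptable. Section 12.2 also says the study should help to design later ones. Whoever designs them needs the uncertainty around the bleeding rate as well as the count.

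**Working it through.** **Nothing to reproduce for safety.** The figure of 15 has no formula behind it, and no precision is stated. The only operating figures in the plan belong to the mortality rule in section 13 (at least 5 deaths in the first 6, or at least 7 in the first 11). Exact enumeration gives suspension probabilities of 0.799 at 70% mortality (plan: 0.80) and 0.292 at 50% (plan: 0.30), so those reproduce. No comparable figure is given for bleeding.

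**Inputs.** n = 15 (12.2); benchmark 20% (section 13); exact 95% interval (12.3, named there for two other endpoints and read in the usual way as two-sided Clopper-Pearson).

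**No bleeds.** The exact upper limit solves (1 − p)^15 = tail probability.
- Two-sided 95%: 1 − 0.025^(1/15) = 0.218.
- One-sided 95%: 1 − 0.05^(1/15) = 0.181.
- Direct check: if the true rate is 20%, the chance of 0/15 is 0.8^15 = 0.035. This is below 5% and above 2.5%, so 20% is excluded one-sided at 5% but not by the two-sided 95% interval.

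**One or more bleeds.** The exact upper limit p for x events solves P(X ≤ x | 15, p) = 0.025 (two-sided) or 0.05 (one-sided).

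| Bleeds | Two-sided 95% interval | One-sided 95% upper limit |
|---|---|---|
| 0/15 | 0 to 21.8% | 18.1% |
| 1/15 | 0.2 to 31.9% | 27.9% |
| 2/15 | 1.7 to 40.5% | 36.3% |
| 3/15 | 4.3 to 48.1% | 44.0% |

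**How easily a reassuring count arises.** At a true rate of 20%, the chance of 0 or 1 bleeds is 0.8^15 + 15 × 0.2 × 0.8^14 = 0.035 + 0.132 = 0.167, about one in six.

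**Sensitivity to interval method, 0/15, two-sided 95%.** Wilson 20.4% and Agresti-Coull 23.9% are above 20%; mid-p 18.1% and Jeffreys 15.2% are below it.

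**Sensitivity to the denominator.** With the twelve patients of section 12.3, 0/12 gives 26.5% two-sided and 22.1% one-sided, so 20% is not excluded either way. With no events, the two-sided exact limit is 20.6% at n = 16 and first falls below 20% at n = 17 (19.5%).

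**The plan's own Beta model.** Its parameters are not stated, so I assumed a range with mean 0.2. After 0/15, the posterior probability that the rate is below 20% is 0.967 for Beta(2, 8), 0.986 for Beta(1, 4) and 0.998 for Beta(0.2, 0.8).

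**The fixed halt rule.** At least 3 bleeds in the first 10 occurs with probability 0.32 at a true 20%, 0.62 at 30% and 0.83 at 40%.

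**The case against.** A reader might infer from the 21.8% that the trial cannot exclude a 20% bleeding rate whatever it observes. The documents do not support that.

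- The question in section 13 runs in one direction, and the one-sided exact limit for 0/15 is 18.1%. Two of the two-sided alternatives are also below 20%.
- The exact interval is borrowed from two other endpoints. The tool that section 13 pairs with 20% is the Beta posterior, and under the assumed priors it puts about 97% to 99.8% probability below 20% after 0/15.
- The plan never undertakes to exclude 20%. That figure triggers a review of accrual and is not a hypothesis for the final analysis. Section 12.2 describes a pilot, disclaims a power calculation, and gives feasible accrual as a further reason for the size.

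A reader might also infer that safety receives counts and nothing else. That is not so either. Measurements get descriptive statistics and change from baseline, bleeding is monitored continuously, and 12.1.2 adds interim assessments after 5 and 10 patients.

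All of this stands and limits the point. It does not remove it. The favourable reading needs exactly zero events in 15 patients: with one bleed, the exact limit is above 20% on either sidedness. The monitoring rules decide whether accrual pauses; they do not say how the final rate is reported. The pilot label explains why there is no power calculation, but it puts no figure behind a claim of adequacy. It is true that anyone can compute an interval from a count, but that is a reason to state it in the plan, where a method is already named for other proportions.

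**Conclusion.** The point holds as a gap in justification and reporting of the primary endpoint. Adequacy for safety is asserted with no precision figure, and event-type safety data have no planned interval although two secondary proportions do. By the exact method at n = 15, zero major bleeds excludes 20% one-sided (18.1%) but not two-sided (21.8%), and a single bleed excludes it on neither (27.9% and about 32%).

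These figures assume 15 treated patients. Section 5.1.1 allows up to 15, and 5.7 provides for replacing patients who are removed, so the number treated may differ. They also assume that the exact 95% interval of 12.3 is the two-sided Clopper-Pearson interval. The posterior probabilities rest on assumed Beta parameters. Nothing here shows an arithmetic error or a need for more patients.

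**What to change.** **Section 12.3.** Add that ISTH major bleeding, any SAE and any grade 3 or higher AE will each be reported as the proportion of treated patients with at least one such event, with an exact 95% confidence interval. State the denominator, and reconcile the twelve patients used for the two Day 28 endpoints with the 15 in 12.2.

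**Section 12.2 and synopsis.** Replace the adequacy claim with a precision statement, for example: *With 15 patients the exact two-sided 95% upper limit for an event rate is 21.8% with no events (one-sided 18.1%) and about 32% with one event.* Do not add a flat statement that the study cannot exclude 20%, since that depends on sidedness and method.

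**Cost.** A few sentences. The data are already collected, and no patients, visits or assays are added. The only loss is that the description of the sample size becomes less favourable.

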12.3 Data Analyses Plans

Descriptive statistics will be calculated for quantitative safety data, as well as change from baseline. Frequency counts will be compiled for classification of qualitative safety data.

Secondary endpoints include reduction in the progression to acute respiratory failure. For patients with a baseline PaO₂/FiO₂ \geq 200: progression of respiratory failure is defined by:

- severe gas transfer deficit (PaO₂/FiO₂ < 200);
- persistent respiratory distress while receiving oxygen (persistent marked dyspnea, use of accessory respiratory muscles, paradoxical respiratory movements);

The rate will be calculated as the proportion of patients who experienced at least one of the events above by day+15 from treatment start.

There are many other secondary endpoints, but two of the most important are: (i) Day 28 overall survival and (ii) Day 28 ventilator free survival, both of which are binary endpoints. Day 28 overall survival will be summarized by the proportion of the twelve patients who are alive at Day 28 after starting treatment, and Day 28 ventilator-free survival will be summarized by the proportion of the twelve patients who are both alive and not using a ventilator at Day 28 after starting treatment. Both proportions will be

accompanied by an exact 95% confidence interval. All other secondary endpoints will be collected and assessed.

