4.1 Inclusion Criteria

1. Adults, ages 18-85 years.
2. Willing and able to provide informed consent prior to performing study procedures unless they have a legally authorized representative (LAR).
3. Documented COVID-19 pneumonia: defined as upper respiratory tract specimen (nasopharyngeal swab (NPS) or viral throat swab) positive for COVID-19 and/or imaging at computed tomography scan suggestive of COVID-19 pneumonia.
4. Confirmed coronavirus (SARS-CoV-2) infection admitted to the hospital, enrolled ≤ 48 hours of need for supplemental oxygen.
5. Currently hospitalized requiring supplemental oxygen.
6. Have severe COVID-19 according to the WHO Interim Guidance with confirmation by real-time RT-PCR assay. The enrollment criteria with one of the following: respiratory distress, RR ≥ 30 beats/min; oxygen saturation level less than 93% in resting state; or partial pressure of oxygen (PaO₂)/oxygen concentration (FiO₂) ≤ 300 mmHg.
WHO, Clinical management of severe acute respiratory infection when Novel coronavirus (nCoV) infection is suspected: Interim guidance. [https://www.who.int/publications-detail/clinical-management-of-severe-acute-respiratory-infectionwhen-novel-coronavirus-\(ncov\)-infection-is-suspected](https://www.who.int/publications-detail/clinical-management-of-severe-acute-respiratory-infectionwhen-novel-coronavirus-(ncov)-infection-is-suspected).
7. Willing and able to participate in all required evaluations and procedures.

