5.4 Duration of Therapy

Each subject in the treatment arm will receive one dose of uproleselan every 12 hours (12 hours apart optimally; acceptable range 10-14 hours) on treatment days 1-7.

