6.2 Study Schedule of Events

Table 4: Events of the Study

	Baseline	Day 1	Day 2	Day 3	Day 4	Day 5	Day 6	Day 7	Day 8	Day 15	Day 28
Eligibility screen	X										
Informed Consent	X										
Medical history	X										
Physical Exam	X	X	X	X	X	X	X	X			
CBC	X ^a	X	X	X	X	X	X	X			
Chemistries	X ^a	X	X	X	X	X	X	X			
ABG	X ^a										
CXR	X ^b										
Biomarkers ^g	X	X	X	X	X	X	X	X		X	X
D-dimer ^g	X			X					X	X	X
Serum pregnancy test	X ^c										
Pulmonary indices ^d	X	X	X	X	X	X	X	X	X	X	X
Uproleselan		X	X	X	X	X	X	X			
Vital Signs ^e		X	X	X	X	X	X	X			
COVID scale	X			X					X	X	X
AE and follow-up ^f		X	X	X	X	X	X	X	X	X	X

Key: CBC-complete blood count; CXR-chest X ray; ABG-arterial blood gas; BP-blood pressure; HR-heart rate; RR-respiratory rate.

Notes:

- a. Laboratory tests performed within 48 hours prior to study enrollment do not need to be repeated at baseline. CBC should be performed daily (until cessation of study therapy) and should be viewed as standard medical care. Arterial blood gas (ABG) measurements, and chest radiographs should be performed per routine medical care. Venous blood gas may be used when ABG unavailable. Patients should continue to have laboratory tests performed (as indicated above) until cessation of study therapy.
- b. Chest X-Ray (CXR): The CXR does not need to be repeated at baseline, if a CXR was done on admission and revealed bilateral infiltrates.
- c. Pregnancy test: Perform in subjects of child-bearing potential, if not already performed this admission for clinical care reasons.
- d. Pulmonary indices will be recorded daily until cessation of drug therapy, and again at day 8, 15 and 28 (if a patient remains hospitalized at that time). Patients who are discharged prior to day 15 or 28 do not need to have pulmonary indices assessed on day 15 or 28.
- e. Vital signs: heart rate, respiratory rate, blood pressure prior to and upon completion of each infusion.
- f. Adverse Event Reporting and Follow-up: Patients will be assessed for adverse events daily during receipt of study therapy, and for 7 days following completion of study drug therapy, provided they remain hospitalized during this 7-day post-therapy period. In addition, patients will be contacted on day 15 and 28 (± 2 days), to assess their clinical status and any active adverse events at that time. This final assessment can be done virtually, by telephone or electronically (email) if the patient cannot be contacted by phone. No in-person visit is required.

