7 MEASUREMENT OF EFFECT

7.1 Safety/Tolerability

AE assessment will be performed for all subjects. The study will use the Common Terminology Criteria for Adverse Events (CTCAE) 5. Physical examination, vital signs, laboratory tests will be performed. Vitals will be taken 10-30 minutes before/after infusion OR at the closest time points possible if not possible in the 10-30 minute period.

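### Vital signs are paired around every infusion, but the only change measure planned for them is change from baseline, which can mask or mimic an acute shift not reported as an adverse event

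*Combined protocol and SAP*

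**What the plan says.** Safety is the primary endpoint (Sections 3.1 and 12.1). Each patient "will receive one dose of uproleselan every 12 hours" on days 1-7 (Section 5.4), and Section 12.2 says that "15 patients who consent to drug administration will be enrolled in the treatment arm".

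Table 4 note e (Section 6.2) calls for "heart rate, respiratory rate, blood pressure prior to and upon completion of each infusion". Section 7.1 describes the timing differently: "Vitals will be taken 10-30 minutes before/after infusion OR at the closest time points possible".

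For analysis, Section 12.3 says "Descriptive statistics will be calculated for quantitative safety data, as well as change from baseline", and for the rest, "Frequency counts will be compiled for classification of qualitative safety data". The synopsis repeats this. Neither place mentions a change across an infusion or a summary by infusion.

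Baseline is defined in Section 6.1.1 for laboratory values only. Vital signs are part of the screening examination (Section 6.1), while the vital-signs row of Table 4 begins on Day 1.

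**The concern.** The schedule collects a matched reading just before each dose, and that reading is the natural control for an acute effect of the dose. The retrospective control cohort receives no infusions and cannot supply one. The only change measure in the plan does not use the pre-infusion reading as its reference.

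Baseline is a poor substitute in this population. Patients enter in an acute state and may qualify on that state itself, for example "respiratory distress, RR ≥ 30 beats/min" (Section 4.1, item 6). Heart rate, respiratory rate and blood pressure can then move over seven days through recovery, deterioration, the background treatments in Table 3 or regression to the mean, with or without the study drug. That movement can cancel a real infusion effect or imitate one. At stake is how clearly a small single-arm safety study can describe the acute tolerability of the infusion.

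**Working it through.** The documents give no figure on this point, so there is nothing to reproduce.

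**Number of pairs.** 2 infusions a day × 7 days = 14 per patient. For 15 fully dosed patients, 15 × 14 = 210 pairs. This is a ceiling, because doses may be missed and Section 7.1 allows readings at the closest possible time.

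**Decomposition.** For any post-infusion reading:

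post − baseline = (pre − baseline) + (post − pre)

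The first term is the drift since baseline and the second is the change across the infusion.

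- If baseline is the Day 1 pre-dose reading, the drift term is zero for the first infusion only. The other 13 of 14 carry drift: 15 × 13 = 195 of 210 pairs, or 93%.
- If baseline is the screening reading, all 14 carry drift.

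**Illustration 1, heart rate (assumed values).** With a true infusion effect of +5 beats/min and drift of 0, −5, −10 or −15, mean change from baseline is +5, 0, −5 or −10. The paired change is +5 each time. For one patient with a rise of 30 after a fall of 10, 20 or 30 since baseline, change from baseline shows +20, +10 or 0; the paired change shows +30.

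**Illustration 2, systolic pressure averaged over 14 infusions (assumed values).** Assume a session-to-session SD of 10 mmHg, a reading SD of 5, a baseline taken at a separate session, and linear drift reaching D at the last infusion. Average drift is D × 7.5/14 = 0.536 D.

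- With a true effect of −5, mean change from baseline is −5.0 for D = 0, −5 + 2.7 = −2.3 for D = +5, and −5 + 5.4 = +0.4 for D = +10. The effect is masked.
- With no effect and D = −10, it is −5.4. An effect is mimicked.
- The paired change has the true mean in every case.
- SE of mean change from baseline: each reading has variance 10² + 5² = 125, so √[(125 + 125/14)/15] = 2.99.
- SE of the mean paired change: √[(2 × 5²)/(14 × 15)] = 0.49.

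The last SE assumes the same infusion effect in every patient. If the effect varies between patients with SD 5, add 25/15 = 1.67 to each variance. The SEs become √(8.93 + 1.67) = 3.3 and √(0.24 + 1.67) = 1.4, so the ratio falls from about 6 to about 2.4. Removal of the drift does not depend on this.

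**Limits of the paired summaries.** One reaction of 30 mmHg in one patient moves the overall mean by 30/210 = 0.14 mmHg, under a third of its SE of 0.49, so a mean alone is not enough. In the other direction, a reading SD of 5 gives a paired difference an SD of √50 = 7.1, and the worst of 14 such differences averages about 12 mmHg in the adverse direction with no drug effect at all.

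**The case against.** A reader might infer that the trial has no other way to see an infusion reaction. The documents do not support that. Adverse events are assessed and physical examinations done on every treatment day (Table 4), all adverse events are recorded (Section 5.2), and attribution takes timing relative to dosing into account (Section 8.3.2). Section 12.3 counts qualitative safety data. A recognised reaction will be counted however mean vital signs are summarised. This stands, and it limits the point to shifts that are not reported as events.

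It can also be said that Section 12.3 promises descriptive statistics as well as change from baseline. If these were tabulated separately for pre- and post-infusion readings with complete pairs, the mean shift could be derived. That is fair, but the plan does not say they will be, and separate tables would show neither the spread of paired changes nor any individual patient's change.

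Nor is it right that no baseline vital signs exist, since screening provides them. What is unstated is whether the screening or the Day 1 pre-dose reading serves as baseline.

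Finally, this is a descriptive pilot. No test, sample size or numerical stopping rule uses mean vital signs, Section 13 allows a halt for any safety reason, and Section 14 provides for regular review of the clinical data. All of this stands, and it makes the point an inexpensive improvement with no bearing on the validity of the study.

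**Conclusion.** The point holds in limited form. The plan collects up to 210 pairs around infusions but states no paired change. The change it does state contains illness drift for at least 13 of 14 infusions, so it can mask or mimic an acute vital-sign shift that is not reported as an adverse event. It does not follow that it will do so.

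The pair count and the decomposition rest on the documents alone. The sizes in beats/min and mmHg are illustrations: the SDs, drifts and effects are assumed. A reader might take away a six-fold gain in precision. That figure requires an identical infusion effect in every patient and falls to about 2.4-fold with a between-patient SD of 5 mmHg. The argument for the paired change is that it removes drift; added precision is secondary.

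**What to change.** In Section 12.3, add that heart rate, respiratory rate and blood pressure will be summarised as post-infusion minus pre-infusion change:

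- by infusion number, with the distribution as well as the mean;
- as a within-patient mean, then summarised across patients;
- as each patient's largest adverse change, read descriptively because the worst of 14 differences is non-zero by chance.

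Keep change from baseline as a separate summary, and state whether the screening or the Day 1 pre-dose reading is the vital-sign baseline.

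Reconcile the timing in Table 4 note e with that in Section 7.1. The choice of time is for the sponsor.

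No new clinical threshold is needed. Exclusion 5 in Section 4.2 does not supply one, because it is defined on two sequential systolic readings at least 4 hours apart and does not carry over to a single post-infusion reading.

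The cost is a few sentences and aligned timing wording. The readings are already scheduled, so no extra data collection is required.
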